### 5.5.4 Echocardiography

Transthoracic echocardiography is used to image the effects of PAH on the heart. An echocardiogram (ECHO) will be performed at Visit 1 and MPV3.

The following parameters will be determined:

- Tricuspid regurgitation (absent, mild, moderate or severe)
- Right ventricular contractility (TAPSE) (mm)
- Pericardial effusion (absent, traces or present)
- Right atrial area (end-systolic) (cm^2)
- Right ventricular end-diastolic area (cm^2)

The clinical significance (yes/no) of any abnormal ECHO findings will be assessed by the investigator.

The following statistical output will be provided:

Table 15.2.4.1.1 Summary of Categorical Echocardiography Parameters – Full Analysis Set

Table 15.2.4.1.2 Summary of Categorical Echocardiography Parameters – Modified Full Analysis Set

Number and percentage of patients will be displayed by HTD and overall at visits V1 and MPV3. Percentage will be based on the number of patients at the specified visit.

Table 15.2.4.2.1 Summary of Numerical Echocardiography Parameters by HTD – Full Analysis Set

Table 15.2.4.2.2 Summary of Numerical Echocardiography Parameters – Full Analysis Set

Table 15.2.4.2.3 Summary of Numerical Echocardiography Parameters by HTD – Modified Full Analysis Set

Table 15.2.4.2.4 Summary of Numerical Echocardiography Parameters – Modified Full Analysis Set

The default summary statistics of ECHO parameters will be presented by HTD and overall at visits V1 and MPV3. The absolute change from baseline will be presented as well. For the changes from baseline a 95% confidence interval will be provided.

Table 15.2.4.2.5 Summary of Numerical Echocardiography Parameters – Modified Full Analysis Set (TAPSE Subgroups)

The default summary statistics of ECHO parameters will be presented by TAPSE subgroup and overall at visits V1 and MPV3. The absolute change from baseline will be presented as well. For the changes from baseline a 95% confidence interval will be provided.

Table 15.2.4.3.1 Incidence of Echocardiography Abnormalities – Full Analysis Set

Table 15.2.4.3.2 Incidence of Echocardiography Abnormalities – Modified Full Analysis Set

Number and percentage of patients will be displayed by HTD and overall in Not CS abnormal and CS abnormal categories. Percentage will be based on the number of patients at the specified visit.

Table 15.2.4.4.1 Shift Table of Echocardiography Results – Full Analysis Set

Table 15.2.4.4.2 Shift Table of Echocardiography Results – Modified Full Analysis Set

Shift tables showing changes in the number and frequency of patients in Not CS abnormal and CS abnormal categories between V1 and MPV3 visits will be provided.

Listing 16.2.3.4 Echocardiography – Enrolled Set

Values of echocardiography tests will be listed.

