Duration of treatment for the individual patient: Maximum treatment duration will depend on the individual HTD. Patients tolerating Dose D (200 mg zamicastat) will take zamicastat for up to 124 days.

Test product, dose and mode of administration: Tablets for oral administration under fed conditions containing 100 mg of zamicastat (BIA 5-1058) each. It is planned to use the following doses:

- | | |
|--------|--|
| Dose A | 50 mg zamicastat once daily (half a tablet of 100 mg) |
| Dose B | 100 mg zamicastat once daily (one tablet of 100 mg) |
| Dose C | 150 mg zamicastat once daily (one and a half tablet of 100 mg) |
| Dose D | 200 mg zamicastat once daily (two tablets of 100 mg) |

Reference therapy, dose and mode of administration: NA

Criteria for evaluation:Primary endpoint; pharmacokinetics:

The following PK parameters (24-hour profile) for zamicastat and its metabolites will be derived after a single dose of 50 mg zamicastat at visit A1 (Day 1):

1. Area under the curve 0-24h (AUC_{0-24h})
2. Maximum plasma concentration (C_{max})
3. Time until C_{max} (t_{max})

The following PK parameters (24-hour profile) for zamicastat and its metabolites will be derived at steady-state at the individual HTD and will be taken at visit MPV3.

4. Area under the curve 0-24h ($AUC_{0-24h,SS}$)
5. Maximum plasma concentration ($C_{max,SS}$)
6. Time until $C_{max,SS}$ ($t_{max,SS}$)
7. Minimum plasma concentration at the end of the dosing interval ($C_{min,SS}$)

The following PK parameter (trough level) will be derived for each dose at steady-state.

8. Minimum plasma concentration at the end of the dosing interval ($C_{min,SS}$)

Additional PK parameters may also be calculated if considered appropriate.

Secondary endpoints:Safety and tolerability endpoints:

1. Adverse events
2. Clinically relevant changes in laboratory parameters (haematology, biochemistry, coagulation, urinalysis, arterial blood gas analysis)
3. Clinically relevant changes in vital signs
4. Clinically relevant changes in ECG
5. Number of digital scars (only in patients with scleroderma)
6. Skin score (only in patients with scleroderma)

Efficacy endpoints:

Change from baseline to MPV3 in:

7. PVR, right atrial pressure (RAP), mPAP, cardiac index (CI) and mixed venous oxygen saturation (SvO_2). Further haemodynamic parameters may also be calculated if considered appropriate.
8. 6-MWT, including Borg dyspnoea score
9. Biomarker (N-terminal pro brain natriuretic peptide [NT-proBNP])

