#### 3.2 Subgroup Analysis

Subgroups will be formed to explore the effects of right ventricular dysfunction at baseline on selected efficacy parameters based on echocardiography results at V1. The subgroups are described in Table 2 below.

Statistical analyses using subgroups will be conducted when specifically referred to in relevant subsections of Section 5, as not every endpoint might need further evaluation using subgroups.

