**Table 2: Subgroup Labels**

Number	Description	Label in TLFs
1	Right ventricular contractility (TAPSE) $\leq$ 17 mm	TAPSE $\leq$ 17 mm
2	Right ventricular contractility (TAPSE) $>$ 17 mm	TAPSE $>$ 17 mm

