## 4.7 Baseline Value

### Baseline value

The baseline value for a variable is defined as the last non-missing value collected before the first IMP intake, unless otherwise specified.

See section 5.4.1 Exposure to IMP for definition of first IMP intake.

**Absolute change from baseline** will be calculated as

$$\text{Absolute Change from Baseline at Visit } X = \text{Value at Visit } X - \text{Baseline Value}$$

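### TAPSE change is tabulated within subgroups cut on the same V1 TAPSE reading that serves as baseline, so opposite subgroup shifts are expected with no drug effect

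*SAP*

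**What the plan says.** SAP section 3.2 gives the purpose and the source of the split: "Subgroups will be formed to explore the effects of right ventricular dysfunction at baseline on selected efficacy parameters based on echocardiography results at V1". SAP Table 2 puts the cut at 17 mm: TAPSE at or below 17 mm against TAPSE above 17 mm.

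SAP section 5.5.4 fixes the timing: "An echocardiogram (ECHO) will be performed at Visit 1 and MPV3". SAP section 4.7 sets the general baseline rule: "The baseline value for a variable is defined as the last non-missing value collected before the first IMP intake, unless otherwise specified". Section 5.5.4 does not specify a different baseline for echo.

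For Table 15.2.4.2.5, on the modified full analysis set, section 5.5.4 states: "The default summary statistics of ECHO parameters will be presented by TAPSE subgroup and overall at visits V1 and MPV3". It adds the absolute change from baseline with a 95% confidence interval. The numerical echo parameters are TAPSE, right atrial area and right ventricular end-diastolic area, and none is left out of this table.

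There is no comparator. The protocol synopsis has "Reference therapy, dose and mode of administration: NA", and SAP section 2.4 confirms that there is no randomisation.

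**The concern.** The only pre-dose echo is at V1, so the V1 TAPSE reading does two jobs: it selects the patients for each subgroup and it is subtracted from their MPV3 value. Patients who fall at or below 17 mm partly because their V1 reading happened to be low will tend to read higher next time. Those above the cut will tend to read lower. No control arm, second pre-dose echo or baseline adjustment is available to remove this.

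The stake is interpretation. The subgroups exist to show how right ventricular dysfunction at baseline bears on the results. For TAPSE, an inert drug is expected to give the pattern a reader would take as benefit in patients with poor right ventricular function: a rise in the low group and none in the high group. The confidence intervals printed beside the means invite that reading.

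**Working it through.** **Inputs from the documents.** Cut at 17 mm (SAP Table 2); classifier is the V1 echo (SAP 3.2); echo at V1 and MPV3 only (SAP 5.5.4); baseline is the last pre-dose value (SAP 4.7); 32 patients planned (SAP 2.6). The plan states no figure on this point, so there is none to reproduce.

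**Inputs assumed.** The documents give no TAPSE mean, SD, V1-MPV3 correlation or size of the modified full analysis set. Assumed: mean 16-20 mm, SD 4 mm (3 and 5 mm as a check), correlation ρ 0.6-0.9, n = 20-32.

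**Formula.** Let V1 and MPV3 TAPSE be bivariate normal with equal mean and SD and no drug effect. Given the V1 value X, the expected change is -(1-ρ)(X - mean). Averaging over each side of the cut, with z = (17 - mean)/SD:

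- at or below 17 mm: expected change = +(1-ρ) × SD × φ(z)/Φ(z)
- above 17 mm: expected change = -(1-ρ) × SD × φ(z)/(1-Φ(z))

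The first is positive and the second negative for every ρ below 1.

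**Central case (mean 18, SD 4, ρ 0.8).** z = -0.25, φ(z) = 0.3867, Φ(z) = 0.4013.

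- Low group: 0.2 × 4 × 0.3867/0.4013 = +0.77 mm
- High group: -0.2 × 4 × 0.3867/0.5987 = -0.52 mm
- Overall: 0.4013 × 0.771 - 0.5987 × 0.517 = 0, so the split creates the shifts and leaves the overall mean change alone.

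**Range at SD 4 mm** (expected change in mm, low group / high group):

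| Mean | ρ = 0.9 | ρ = 0.8 | ρ = 0.6 |
|---|---|---|---|
| 16 | +0.26 / -0.39 | +0.52 / -0.77 | +1.03 / -1.54 |
| 18 | +0.39 / -0.26 | +0.77 / -0.52 | +1.54 / -1.03 |
| 20 | +0.53 / -0.16 | +1.06 / -0.31 | +2.13 / -0.62 |

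With SD 3 or 5 mm, the low-group shift runs from +0.18 to +2.43 mm.

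**How often the intervals mislead.** Null trials were simulated, 20,000 per setting, with t-based 95% intervals for the mean change and at least 2 patients in the group. The settings were means 16, 17, 18, 19 and 20; ρ 0.9, 0.8, 0.7 and 0.6; n = 20, 26 and 32; SD 4 mm.

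- Low-group interval wholly above zero: 6.9% (mean 16, ρ 0.9, n 20) to 33.6% (mean 19, ρ 0.6, n 32); nominal 2.5%.
- High-group interval wholly below zero: 5.2% to 32.8%; nominal 2.5%.
- Overall interval wholly above zero: 2.2% to 2.8%, as it should be.
- Low-group mean above zero: 69.0% to 95.3%, so about 5-31% of null trials show no rise.
- Central case, low-group interval above zero: 12%, 15% and 18% for n = 20, 26 and 32.
- SD 3 and 5 mm (means 16, 18, 20; ρ 0.9, 0.6; n 20, 32): low-group rate 6.6% to 33.6%.

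Requiring at least 3 patients in each subgroup, with n = 32, mean 17 and SD 4, the two means have the opposite signs described in 87%, 73% and 58% of null trials for ρ = 0.6, 0.8 and 0.9. At least one subgroup interval excludes zero in 50%, 30% and 20%, against about 10% nominal for two intervals (1 - 0.95² = 9.75%).

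**The case against.** The strongest reply is about weight. This is one row of one table among 150 in an analysis the SAP calls explorative, with no subgroup test planned and a pharmacokinetic primary endpoint. The size rests on assumed TAPSE parameters and spans about eightfold. In the central case 82-88% of null trials would not show a low-group interval wholly above zero. PAH is progressive, so an overall drift could give both subgroups the same sign. Without a control arm no change score here can be credited to the drug on its own. The table shells are a separate appendix that was not available, and SAP section 4.2 allows important definitions to be footnoted.

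Most of this is fair, and it limits the point to the TAPSE row. It does not remove it. Exploratory status answers power and multiplicity, whereas this is a bias of known direction. A larger sample makes the false signal more frequent: 12% rises to 18% between n = 20 and n = 32 in the central case. A common drift adds to both subgroups and leaves the gap between them, 0.77 + 0.52 = 1.29 mm in the central case. The overall change has the usual ambiguity of a single-arm study, but the subgroup changes carry an extra artefact made by the split itself. A shell might carry a warning, but the SAP text requires none.

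The point does not extend directly to right atrial or right ventricular area, or to the catheterisation and walk-test tables by TAPSE subgroup. There a similar bias arises only as far as their baseline visit-to-visit variation is correlated with that of V1 TAPSE.

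**Conclusion.** The concern holds. The direction follows from the plan's own definitions, given no drug effect, no time trend, similar SDs at the two visits and a V1-MPV3 correlation below 1. It is a statement about expectation, and a single trial may not show it. The millimetre shifts and error rates in the working are illustrative, because they rest on TAPSE values the documents do not give. Even at the mildest setting simulated at SD 4 mm, the low-group interval is wholly above zero at more than twice its nominal rate (6.9% against 2.5%). The subgroup TAPSE changes and their intervals therefore cannot be read as effects of zamicastat by baseline right ventricular function. The row should be changed; the overall echo results need no correction on this account.

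**What to change.** Remove the TAPSE change row from Table 15.2.4.2.5 and add one sentence to SAP section 5.5.4, for example:

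*Change from baseline by TAPSE subgroup will be presented for ECHO parameters other than TAPSE; TAPSE will be shown at V1 only, to describe the subgroups.*

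Showing V1 only matters, since V1 and MPV3 means side by side would let a reader rebuild the same change. TAPSE change stays in Tables 15.2.4.2.1 and 15.2.4.2.3 (by highest tolerated dose) and in 15.2.4.2.2 and 15.2.4.2.4 (all patients in the full and modified full analysis sets).

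If the team prefers to keep the row, add a footnote:

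*Subgroups are defined by the V1 TAPSE value used as baseline; opposite shifts in the two subgroups are expected from regression to the mean and are not evidence of a treatment effect.*

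The cost is one SAP sentence and one row, or one footnote, in one table shell. No new data or tables are needed. Removal loses one exploratory row; the individual values remain in Listing 16.2.3.4.

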### 5.5.5 New York Heart Association/World Health Organisation Functional Class (NYHA/WHO)

Classification of functional status of patients will be performed at Visit 1 and at visit MPV3/EDV by the investigator by using the NYHA/WHO classification system defined below.

**Table 6: NYHA/WHO Classes**

Class	Description
Class I	Patients with pulmonary hypertension but without resulting limitation of physical activity. Ordinary physical activity does not cause undue dyspnoea or fatigue, chest pain or near syncope.
Class II	Patients with pulmonary hypertension resulting in a slight limitation of physical activity. They are comfortable at rest. Ordinary physical activity causes undue dyspnoea or fatigue, chest pain or near syncope.
Class III	Patients with pulmonary hypertension resulting in marked limitation of physical activity. They are comfortable at rest. Less than ordinary activity causes undue dyspnoea or fatigue, chest pain or near syncope.
Class IV	Patients with pulmonary hypertension with inability to carry out any physical activity without symptoms. These patients' manifest signs of right heart failure. Dyspnoea and/or fatigue may even

The following statistical output will be provided:

Table 15.2.5.1.1 Summary of NYHA/WHO Functional Class – Full Analysis Set

Table 15.2.5.1.2 Summary of NYHA/WHO Functional Class – Modified Full Analysis Set

Number and percentage of patients will be displayed by HTD and overall in each NYHA/WHO functional class. Percentage will be based on the number of patients at the specified visit.

Table 15.2.5.2.1 Shift Table of NYHA/WHO Functional Class – Full Analysis Set

Table 15.2.5.2.2 Shift Table of NYHA/WHO Functional Class – Modified Full Analysis Set

Shift tables showing changes in the number and frequency of patients with respect to the NYHA/WHO functional class between V1 and MPV3/EDV will be provided.

Listing 16.2.3.5 NYHA/WHO Functional Class – Enrolled Set

NYHA/WHO functional class data will be listed by visit.

### 5.5.6 Quality of Life (SF-36v2)

The 36-item Short Form Survey version 2 (SF-36v2) is used to assess the quality of life. The questionnaire will be completed by the patient at Visit 1 and at MPV3.

SF-36v2 asks 36 questions (items) to measure functional health and well-being from the patient's point of view. All but one (question 2) of the 36 items will be used to score the eight SF-36v2 health domains:

- Physical Functioning (PF)
- Role Limitations due to Physical Health (RP)
- Bodily Pain (BP)
- General Health (GH)
- Vitality (VT)
- Social Functioning (SF)
- Role Limitations due to Emotional Health (RE)
- Mental Health (MH).

A total score will be calculated for each SF-36v2 health domain by taking the sum of the corresponding responses and rescaling it to a range of 0 to 100, where 100 represents the best possible result. Each domain will then be standardised using a general population norm.

The scores of the eight health domains will be used to calculate a physical component summary (PCS) and mental component summary (MCS) score using coefficients based on a principal components analysis of the SF-36v2 domain scores in the general population. The PCS and MCS are summary measures that represent the overall physical and mental health of the patient, with higher scores representing better outcomes.

A subset of items from six domains (PF, RE, SF, BP, MH, VT) will be used to calculate a Utility Index Score, which rates the overall health state from 0.0 (worst health state) to 1.0 (best health state). The updated (SF-6D R2) Utility Index Score will be summarised.

Optum PRO CoRE will be used to generate the following scores:

- SF-36v2 domain scores (0-100 scale)
- SF-36v2 domain scores based on the 2009 US general population norms
- PCS and MCS scores based on the 2009 US general population norms
- SF-6D R2

In addition, interpretations for the norm-based SF-36v2 health domains and PCS and MCS scores will be provided based on benchmarks from the general population cardiac patients:

- “Well Below”, if the norm-based score is 10 points or more below the benchmark;
- “Below”, if the norm-based score is from 5 to 9 points below the benchmark;
- “Same or Better”, if the norm-based score is less than 5 points below the benchmark.

The following statistical output will be provided:

Table 15.2.6.1.1 Summary of SF-36v2 Domain Scores by HTD – Full Analysis Set

Table 15.2.6.1.2 Summary of SF-36v2 Domain Scores – Full Analysis Set

Table 15.2.6.1.3 Summary of SF-36v2 Domain Scores by HTD – Modified Full Analysis Set

Table 15.2.6.1.4 Summary of SF-36v2 Domain Scores – Modified Full Analysis Set

The default summary statistics of SF-36v2 results will be presented by HTD and overall at visits V1 and MPV3. The absolute change from baseline will be presented as well. For the changes from baseline a 95% confidence interval will be provided.

Table 15.2.6.2.1 Summary of Norm-Based SF-36v2 Domain Scores by HTD – Full Analysis Set

Table 15.2.6.2.2 Summary of Norm-Based SF-36v2 Domain Scores – Full Analysis Set

Table 15.2.6.2.3 Summary of Norm-Based SF-36v2 Domain Scores by HTD – Modified Full Analysis Set

Table 15.2.6.2.4 Summary of Norm-Based SF-36v2 Domain Scores – Modified Full Analysis Set

The default summary statistics of SF-36v2 results based on 2009 US norms will be presented by HTD and overall at visits V1 and MPV3. The absolute change from baseline will be presented as well. For the changes from baseline a 95% confidence interval will be provided.

Table 15.2.6.3.1 Summary of SF-36v2 Utility Index Scores by HTD – Full Analysis Set

Table 15.2.6.3.2 Summary of SF-36v2 Utility Index Scores – Full Analysis Set

Table 15.2.6.3.3 Summary of SF-36v2 Utility Index Scores by HTD – Modified Full Analysis Set

Table 15.2.6.3.4 Summary of SF-36v2 Utility Index Scores – Modified Full Analysis Set

The default summary statistics of Utility Index scores will be presented by HTD and overall at visits V1 and MPV3. The absolute change from baseline will be presented as well. For the changes from baseline a 95% confidence interval will be provided.

Table 15.2.6.4.1 Summary of SF-36v2 Cardio Benchmark Interpretation – Full Analysis Set

Table 15.2.6.4.2 Summary of SF-36v2 Cardio Benchmark Interpretation – Modified Full Analysis Set

Number and percentage of patients will be displayed by HTD at visits V1 and MPV3. Percentage will be based on the number of patients at the specified visit.

Table 15.2.6.5.1 Shift Table of SF-36v2 Cardio Benchmark Interpretation – Full Analysis Set

Table 15.2.6.5.2 Shift Table of SF-36v2 Cardio Benchmark Interpretation – Modified Full Analysis Set

Shift tables showing changes in the number and frequency of patients with respect to the Cardio benchmark interpretation between V1 and MPV3 will be provided.

Figure 15.2.2.1 Norm-Based SF-36v2 Domain Scores by Visit – Full Analysis Set

Figure 15.2.2.2 Norm-Based SF-36v2 Domain Scores by Visit – Modified Full Analysis Set

The means of norm-based SF-36v2 domain scores will be presented by HTD at visits V1 and MPV3 using a bar chart. A reference line will be included for the average score in the general population.

Figure 15.2.3.1 SF-36v2 Cardio Benchmark Interpretation by Visit – Full Analysis Set

Figure 15.2.3.2 SF-36v2 Cardio Benchmark Interpretation by Visit – Modified Full Analysis Set

The numbers of patients in each cardio benchmark interpretation category will be displayed by HTD for each domain at visits V1 and MPV3 using a stacked bar chart.

Listing 16.2.3.6 SF-36v2 – Enrolled Set

Summary scores based on the SF-36v2 survey results will be listed.

## 5.6 Analysis of Safety Endpoints

Safety will be assessed by evaluation of the following variables:

- Adverse events
- Clinically relevant changes in laboratory parameters (haematology, biochemistry, coagulation, urinalysis, arterial blood gas analysis)
- Clinically relevant changes in vital signs
- Clinically relevant changes in ECG
- Physical examination findings
- Number of digital scars (only in patients with scleroderma)
- Modified Rodnan Skin score (only in patients with scleroderma)

### 5.6.1 Adverse Events

AEs will be coded according to latest Medical Dictionary for Regulatory Activities (MedDRA®) Version 22.0.

Adverse events' data include:

- adverse event name
- start/stop dates
- ongoing
- severity (mild, moderate, severe)
- relationship (not related, unlikely, possible, probable, definite)
- action taken with study medication (dose not changed, dose reduced, drug interrupted, drug withdrawn, not applicable, unknown)
- other actions (none, medication required, tests required, withdrawn from the study, hospitalisation required or prolonged, other specification)

- outcome of event (recovered/resolved, recovering/resolving, not recovered/not resolved, recovered/resolved with sequelae, fatal, unknown)
- AE of special interest (yes or no)
- seriousness (yes or no)
- start/stop dates of drug interruption

All AEs will be presented in listings.

Summaries of adverse events will include AEs defined as **treatment-emergent adverse events (TEAEs)**, defined as AEs with the first onset or worsening after the first IMP intake and not more than 14 days after the last IMP intake.

If the start date of an AE is incomplete or missing, it will be assumed to be treatment-emergent except if the incomplete start date or the stop date indicates that the event started or ended prior to the first IMP intake or started later than 14 days after last IMP intake.

AEs will be further assigned to the following categories:

- **Serious Adverse Events (SAEs):** defined as AEs considered by the investigator as serious.
- **Adverse Event of Special Interest (AESIs):** defined as AEs assessed by the investigator as being of special interest.
- **Related TEAEs:** defined as AEs assessed as being “Possible”, “Probable” or “Definite” to IMP and include the events with missing IMP relationship assessment.
- **Unrelated TEAEs:** defined as AEs assessed as being “Not related” or “Unlikely” to be related to IMP.
- **Severe TEAEs:** defined as AEs assessed as being “Severe” in intensity and include the events with missing severity assessment.
- **TEAEs leading to down-titration:** defined as AEs where “Action taken with study medication” is indicated as “dose reduced”.
- **TEAEs leading to discontinuation:** selected as those events where “Action taken with study medication” is indicated as “drug withdrawn” or “other actions” is “discontinued from study”.
- **TEAEs leading to death:** selected as those events where outcome of event is indicated as “fatal”.

Adverse events will be assigned to IMP dose groups based on the prescribed IMP dose at the date of AE onset. AEs with an onset date on the same day as a down-titration will be assigned to the previous dose. If the AE onset date is incomplete such that it could belong to more than one prescribed dose, the AE will be assigned to all such doses.

The following statistical output will be provided:

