10.3 Selection of Doses in the Study

10.3.1 Selection and timing of dose for each patient

Each patient will start treatment with 50 mg zamicastat once daily (Dose A) at visit A1 and will be up-titrated step by step to the individual HTD i.e. up to 200 mg zamicastat once daily. The 100 mg tablet has to be split at the break score in two equal halves using a pill splitter.

Table 2: Dosage regimen

	Daily dose
Dose A	50 mg (half a tablet of 100 mg)
Dose B	100 mg (one tablet of 100 mg)
Dose C	150 mg (one and a half tablet of 100 mg)
Dose D	200 mg (two tablets of 100 mg)

Each next dose will start after 14 days of treatment if the previous dose was considered safe by the investigator. The up-titration is based on the following safety criteria, including but not limited to:

- Absence of symptomatic and/or clinically relevant orthostatic hypotension
- SBP > 95 mmHg or DBP > 50 mmHg
- Absence of clinically significant changes in ECG parameters (heart rate, P-R interval, QRS duration, QT and QTc interval)
- Absence of clinically significant hypersensitivity/skin allergic reactions

Patients not fulfilling the criteria for up-titration after 14 days of treatment with 50 mg zamicastat have to be withdrawn from the trial.

If the patient's next dose will not be tolerated by the patient, the dose has to be down-titrated to his/her previous dose and this dose will be considered as the individual HTD, if tolerated by the patient. Treatment at the individual HTD will be for 42 days during the maintenance period.

Zamicastat has to be taken in the morning after breakfast. The patient must not take the tablet at home on visit days (A3/B3/C3/D3, MPV1, MPV2 and MPV3).

In case a patient missed to take the dose after breakfast, (s)he should take the dose after lunch. The next dose should be taken as scheduled. If the dose was missed after lunch too, the dose for this day has to be skipped.

Patients taking 150 mg or 200 mg of zamicastat and who will not participate in the extension study will take 100 mg zamicastat for 14 days.

In case a patient will discontinue the trial early due to the occurrence of an AE, down-titration is not mandatory, but at the investigator's discretion. In case down-titration is recommended by the investigator, it should follow the same procedure as described above.

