12.2 Documentation and Treatment of Adverse Events by the Investigator

All AEs, including SAEs, occurring within the period of observation for the clinical study must be recorded. The period of observation for the collection of AEs extends from the time when the patient gives informed consent until the date of final visit.

Medical conditions that are diagnosed at the screening visit will only be documented as AEs, if they are known to have started or are suspected to have started after the ICF has been signed. All other medical findings at the medical examination at the screening visit will be documented as medical history. Medical judgement should be exercised to estimate if a condition is likely to have started between the signing of the informed consent and the date/time of the medical examination.

Any AE that is still ongoing after final visit will be left as ongoing in the eCRF. However, the investigator will continue to follow up ongoing SAEs and record information in the source documents and on the Follow-Up SAE Form, until resolution or no further improvement can be expected.

There is no time limit on collection of SAEs that are considered related to study drug. If the investigator detects a SAE of a study patients after the last visit, and considers the event possibly related to prior study treatment or procedures, he/she should contact one of the Bial safety managers to determine how the event should be documented and reported.

At each visit, the investigator should ask the study patient in a non-leading manner about the state of his/her health in order to elicit information on AEs which may have occurred since the last visit. Any clinically significant observations made during the visit itself also constitute AEs.

The AEs must be documented as soon and as completely as possible on the “Adverse Events” pages in the eCRF. Follow up information must be entered as soon as available.

The following will also be specified:

- Action taken with IMP: dose not changed, dose reduced, drug interrupted, drug withdrawn, not applicable, unknown.
- Other actions (none, medication required, tests required, hospitalisation required or prolonged, withdrawn from the trial, other – please specify).
- Outcome of event (fatal, not recovered/not resolved, recovered/resolved, recovered/resolved with sequelae, recovering/resolving, unknown) and date of outcome.
- Seriousness: yes or no (criteria for SAE see above).
- Severity.
- Causal relationship to IMP

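### The rule for TEAEs leading to discontinuation searches for an 'other actions' value that neither document lists, so AEs that ended participation can be left out

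*SAP*

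**What the plan says.** SAP 5.6.1 first lists the data collected for each adverse event. Two fields matter here:

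- The drug action: "action taken with study medication (dose not changed, dose reduced, drug interrupted, drug withdrawn, not applicable, unknown".
- The other actions: "other actions (none, medication required, tests required, withdrawn from the study, hospitalisation required or prolonged, other specification".

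Protocol 12.2 gives the second field in slightly different words: "Other actions (none, medication required, tests required, hospitalisation required or prolonged, withdrawn from the trial, other – please specify".

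The same SAP section then defines two categories from these fields. TEAEs leading to down-titration are "defined as AEs where “Action taken with study medication” is indicated as “dose reduced". TEAEs leading to discontinuation are "selected as those events where “Action taken with study medication” is indicated as “drug withdrawn” or “other actions” is “discontinued from study".

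Protocol 13.4.3 promises a summary of TEAEs leading to discontinuation from the study, which is wider than stopping the drug. The SAP delivers it in Table 15.3.1.8, in three rows of Table 15.3.1.1 (all, serious and related) and in Listing 16.2.4.1.6.

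Protocol 10.3.1 also covers a patient who leaves early because of an AE. For that patient "down-titration is not mandatory, but at the investigator's discretion", and "In case down-titration is recommended by the investigator, it should follow the same procedure as described above". That procedure is for patients on 150 or 200 mg.

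**The concern.** The discontinuation rule has two arms joined by 'or'. The first catches events for which the drug was withdrawn. The second is meant to catch events for which the patient left the study, whatever the drug-action field says. The value it looks for is not in the list printed a few lines above it, nor in the protocol's list.

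If the second arm is empty, a summary meant to cover leaving the study becomes a summary of one drug-action code. Removing an arm from an 'or' rule can only lower the count, so any error makes tolerability look better. Tolerability is a secondary objective, and the number of patients who leave because of an AE is one of its main measures.

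The design makes the gap more than theoretical. A patient who leaves for an AE may still be given a lower dose for a time. SAP 4.6 provides for this with a down-titration period that can begin the day after the early discontinuation visit. For such a patient 'dose reduced' is a plausible entry in the drug-action field, and the study withdrawal would then show only in 'other actions'.

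**Working it through.** The plan states no figure to reproduce. The check applies the rule to every combination of documented values.

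**Inputs (SAP 5.6.1)**

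- Drug action, 6 values: dose not changed, dose reduced, drug interrupted, drug withdrawn, not applicable, unknown.
- Other actions, 6 values: none, medication required, tests required, withdrawn from the study, hospitalisation required or prolonged, other specification.
- Combinations: 6 × 6 = 36, taking one value per field.

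**Rule as written:** drug action = 'drug withdrawn', or other actions = 'discontinued from study'.

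- First arm: 1 × 6 = 6 combinations.
- Second arm: 0 combinations, because the value is not among the six.
- Total: 6 of 36.

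**Rule with the listed value:** drug action = 'drug withdrawn', or other actions = 'withdrawn from the study'.

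- First arm 6, second arm 6, overlap 1.
- Total: 6 + 6 − 1 = 11 of 36.

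**The six combinations that contain 'withdrawn from the study'**

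| Drug action | Rule as written | Rule with listed value |
|---|---|---|
| drug withdrawn | selected | selected |
| dose reduced | down-titration only | both categories |
| dose not changed | not selected | selected |
| drug interrupted | not selected | selected |
| not applicable | not selected | selected |
| unknown | not selected | selected |

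The literal rule finds 1 of these 6, and the corrected rule finds all 6. These are counts of possible codings, not of patients, and they say nothing about how often each coding occurs. If the form allows several 'other actions' per event, the result for the second arm is the same: the searched value is still not on the list.

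**Size per patient.** SAP 5.6.1 bases AE percentages on the safety set. Assuming all 32 planned patients are dosed, one missed patient is 1/32 = 3.1 percentage points, two are 2/32 = 6.2, and three are 3/32 = 9.4. The lower end of the range is zero.

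**The case against.** The strongest reply is that nobody would program the rule by exact string. The documents treat the two terms as equivalents: protocol 9.4.2 and SAP 5.1.1 both define withdrawals as patients who discontinued after first IMP intake. The list has only one value for leaving the study, so there is only one sensible mapping. The eCRF itself is not among the documents, and the two lists differ enough in wording to look paraphrased, so the stored value is unknown. All this is fair, and it is why the under-count is only a possibility. It does not make the rule right. The SAP is the specification, and its value should match the data it describes.

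A reader might infer that tapered patients are always counted only as down-titrations. The documents do not support that. Neither says what to record in the drug-action field when a taper follows an AE-driven exit, and if 'drug withdrawn' is entered the first arm selects the event. The route is also narrow. The taper concerns only 150 and 200 mg and is discretionary after an AE. A patient who fails a higher dose during dose finding and continues on the previous one is correctly coded as 'dose reduced'.

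A reader might also want the loss as a share of all AE discontinuations. The documents give no expected number of these, so any such percentage would be invented.

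Finally, the events do not vanish. All AEs are listed, Table 15.1.4 and Listing 16.2.1.1.1 give termination reasons, and protocol 15.4 provides for queries on inconsistent data. These outputs would show that a patient left for an AE. However, Table 15.1.4 does not show which TEAE, by SOC and preferred term or by concurrent dose, and that is the content of Table 15.3.1.8.

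**Conclusion.** The mismatch is a fact: the rule selects on a value that appears in neither document's list. Followed exactly, the second arm selects nothing, and an AE marked as a study withdrawal without 'drug withdrawn' is left out of the discontinuation outputs. Whether any event is actually lost depends on two things the documents do not settle: how the rule is programmed, and what investigators record as the drug action. If the synonym is mapped, or 'drug withdrawn' is recorded each time, the under-count is zero. If neither happens, each missed patient is about 3.1 percentage points, assuming a safety set of 32.

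The misplacement of tapered patients is one possible route, conditional on 'dose reduced' being entered for a patient leaving from 150 or 200 mg. No primary endpoint or analysis set is affected. The point deserves correction because the error can go in only one direction and is almost free to remove.

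**What to change.** Three changes to SAP 5.6.1:

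1. Replace 'discontinued from study' in the rule with the value actually stored in the eCRF ('withdrawn from the study' or 'withdrawn from the trial'), and use the same flag for Tables 15.3.1.1 and 15.3.1.8 and Listing 16.2.4.1.6.
2. State that an event may fall in both the down-titration and the discontinuation category. The present definitions do not exclude this, so no rule is needed on which category takes priority.
3. Check the flagged events, patient by patient, against the termination-page reason 'Intolerable adverse event(s)' listed in SAP 5.1.1, and explain any difference. This is a check and not a second definition, since an AE may also lie behind another termination reason.

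The cost is a few sentences in the SAP, a small change to one derived flag and a short reconciliation. The number of reported discontinuation TEAEs can stay the same or rise, but it cannot fall through the change of value.
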